Our aim is to evaluate the safety and efficacy of preoperative zoledronic acid treatment on bone turnover in postmenopausal women and older men undergoing RYGB or SG. We will examine 6-month postoperative changes in serum CTX and P1NP, markers of bone turnover, after a preoperative infusion of zoledronic acid in an open-label fashion. We will also employ and refine a perioperative protocol of calcium and vitamin D supplementation, with serial monitoring of serum calcium levels.

Hypothesis: Zoledronic acid safely and effectively inhibits the increases in CTX and P1NP after RYGB and SG.

Aim 2

Our aim is to assess early changes in bone density, and estimated bone strength after preoperative zoledronic acid in postmenopausal women and older men undergoing RYGB or SG. We will utilize dual-energy x-ray absorptiometry (DXA) and quantitative computed tomography (QCT) to preliminarily assess skeletal changes 6 months after RYGB and SG.

Hypothesis: Zoledronic acid attenuates early RYGB- and SG-induced bone loss

III. Subject Selection

This open-label, single arm pilot study is designed as a proof-of-concept study to demonstrate feasibility, determine efficacy of surrogate endpoints (e.g. suppression of bone turnover markers), and to obtain preliminary data about early (6 month) bone density-outcomes.

Inclusion criteria:

1. Women or men planning to receive RYGB or SG surgery
2. Women must be aged ≥ 25 years AND postmenopausal by either of the following criteria
> 36 months since last spontaneous menses; or
> 36 months since hysterectomy, plus serum FSH > 40 units/liter
3. Men must be aged ≥ 50 years

Exclusion criteria:

1. Prior bariatric surgery
2. Weight \geq 400 lbs (due to limitations of bone imaging equipment)
3. Liver disease (AST or ALT $>$ 2 x upper normal limit)
4. Renal disease (serum creatinine $>$ 2.0 mg/dL or eGFR $<$ 35 ml/min)
5. Hypercalcemia (Ca $>$ 10.5 mg/dL) or hypocalcemia (Ca $<$ 8.5 mg/dL)
6. Hypomagnesemia (Mg $<$ 1.7 mg/dL)
7. Serum 25-OH vitamin D $<$ 20 ng/mL

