All subjects will be informed of their rights under the Health Insurance and Portability and Accountability Act of 1996 per federal law and hospital policy. The consent form describes what protected health information from the research study may be used or shared with others. Data collected strictly for research purposes are stored in locked files and on computers with passwords required for access. Data will be entered into the Partners-approved secure REDCap database system. When the data are published, no names or other materials that allow identification of an individual will be used.

Study physicians and staff will monitor subjects closely. Routine safety measures (e.g. renal function, calcium levels) will be assessed as described in the research plan and reviewed by a physician in real-time. The study physicians and the study staff will also meet on a weekly basis to discuss any issues relating to adverse events, safety data and outcome data. At the discretion of the study physician, any laboratory or physical exam abnormalities can be cause for discontinuation. If a subject experiences an adverse event, we will ensure necessary medical treatment and will provide that treatment, free of cost if necessary, within our institution.

Although rates of hypocalcemia are rare in osteoporosis studies, RYGB and SG patients might be at greater risk of developing hypocalcemia in response to zoledronic acid. Nevertheless, we expect these risks to be small. All study subjects will be required to have normal serum calcium, magnesium, 25-hydroxyvitamin D, and renal function at study entry. Patients taking loop diuretics will be excluded due to increased risk of hypocalcemia with zoledronic acid with concomitant use.

In addition to the precautions being taken with all study subjects, postoperative serum chemistries will be monitored closely at multiple timepoints as described below:

Postoperative serum calcium and 25OHD levels will be monitored closely at 2-week, 12-week, and 6-month timepoints, as indicated in the research protocol.

- Laboratory results obtained during the follow-up visits will be approached according to the following algorithm:
 - Serum 25OHD < 30 ng/mL with corrected serum calcium within normal range:
 - Serum 25OHD 20-30 ng/dL: increase vitamin D intake by 2000 IU
 - Serum 25OHD < 20 ng/dL: increase vitamin D intake by 2000 IU daily and add ergocalciferol 50,000 IU three times weekly for 3 weeks
 - Hypocalcemia:

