 - Grade 1, corrected calcium 8.0-8.4 mg/dL:
 - if without symptoms and if vitamin D is to be increased in response to 25OHD level (see above), no additional treatment beyond the increase in vitamin D supplement; repeat serum calcium in 1 week and increase total daily calcium intake by 500 mg (up to a maximum daily intake of 2500 mg/day) if still \leq 8.4 mg/dL
 - if symptomatic or if 25OHD level already at goal of 30 ng/mL, increase total daily calcium intake by 500 mg (up to a maximum daily intake of 2500 mg/day); repeat serum calcium in 1 week
 - Grade 2, corrected calcium 7.0-7.9 mg/dL:
 - if without symptoms and if vitamin D is to be increased in response to 25OHD level (see above), increase total daily calcium intake by 500 mg (up to a maximum daily intake of 2500 mg/day) and increase vitamin D supplement as above; repeat serum calcium in 1 week
 - if symptomatic or if 25OHD level already at goal of 30 ng/mL or if already at maximum daily calcium intake, also add calcitriol 0.25 mcg

once daily (if 7.5-7.9 mg/dL) or twice daily (if 7.0-7.4 mg/dL); repeat serum calcium in 1 week

- If corrected calcium still <8.0 mg/dL at 1-week recheck, increase calcitriol by 0.25 mcg daily and repeat
- Grade 3 (corrected calcium 6.0-6.9 mg/dL) or grade 4 (corrected calcium <6.0 mg/dl or severe symptoms): refer to physician for IV calcium and other evaluation and treatment

Finally, renal function will be monitored closely and patients are required to have an estimated GFR >35 (mL/min) to receive study drug. Additionally, no subject will be enrolled if they have any major dental work planned during the course of the study, and all subject complaints of thigh or groin pain will be immediately evaluated to rule out an incomplete femur fracture. The risks of phlebotomy will be minimized by careful attention to proper technique.

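### Both vitamin D action thresholds in the section IX safety algorithm are printed in ng/dL where ng/mL is evidently meant, a factor of 100

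*Combined protocol and SAP*

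**What the plan says.** The algorithm for follow-up laboratory results is in section IX, Data and Safety Monitoring Plan. Its vitamin D step has a header and two action lines.

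- Header: "Serum 25OHD < 30 ng/mL with corrected serum calcium within normal range".
- First action line: "Serum 25OHD 20-30 ng/dL: increase vitamin D intake by 2000 IU".
- Second action line: "Serum 25OHD < 20 ng/dL: increase vitamin D intake by 2000 IU daily", together with a three-week course of ergocalciferol 50,000 IU, three doses a week.

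The hypocalcemia steps that follow refer back to this one. For asymptomatic grade 1 the rule is "if without symptoms and if vitamin D is to be increased in response to 25OHD level (see above), no additional treatment beyond the increase" in the supplement, with calcium rechecked after a week. The alternative grade 1 branch is "if symptomatic or if 25OHD level already at goal of 30 ng/mL, increase total daily calcium intake by 500 mg". The asymptomatic grade 2 branch raises calcium intake, then adds "and increase vitamin D supplement as above; repeat serum calcium in 1 week".

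Outside section IX, the only other 25OHD threshold is the exclusion criterion in section III: "Serum 25-OH vitamin D $<$ 20 ng/mL".

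**The concern.** The header and the two lines under it use different units for the same quantity. The numbers 20 and 30 match the exclusion limit and the treatment goal, but the unit attached to them does not. Taken literally, the lines that tell staff what to do never apply at the concentrations the header describes.

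These lines are operative treatment triggers, applied at weeks 2 and 12 and month 6. They concern any participant whose vitamin D is below goal, not only those who become hypocalcemic. Entry requires 25OHD of at least 20 ng/mL, so someone can join the trial already inside the intended 20-30 ng/mL band.

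The text also has uses beyond bedside decisions. Aim 1 includes refining the perioperative calcium and vitamin D regimen, the pilot is meant to inform a larger trial, and the DSMB reviews protocol adherence. Adherence to these two lines cannot be judged against thresholds wrong by a factor of 100.

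**Working it through.** **Inputs**

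- Header of the vitamin D step: below 30 ng/mL, corrected calcium normal (section IX).
- Action lines as printed: 20-30 ng/dL and below 20 ng/dL (section IX).
- Vitamin D goal in the grade 1 and grade 2 branches: 30 ng/mL (section IX).
- Exclusion limit: below 20 ng/mL (section III).

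**Conversion.** 1 dL = 100 mL, so x ng/mL = 100x ng/dL and y ng/dL = y/100 ng/mL.

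- 20 ng/dL = 20/100 = 0.2 ng/mL.
- 30 ng/dL = 30/100 = 0.3 ng/mL.

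The printed lines therefore cover 0.2-0.3 ng/mL and below 0.2 ng/mL. Any value above 0.3 and below 30 ng/mL meets the header and neither line.

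**Test values, with normal corrected calcium**

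| 25OHD (ng/mL) | In ng/dL | Header met? | Printed 20-30 ng/dL line | Printed <20 ng/dL line | Line that applies if the unit is ng/mL |
|---|---|---|---|---|---|
| 10 | 1000 | yes | no | no | <20 |
| 15 | 1500 | yes | no | no | <20 |
| 20 | 2000 | yes | no | no | 20-30 |
| 25 | 2500 | yes | no | no | 20-30 |
| 29.9 | 2990 | yes | no | no | 20-30 |

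As printed, none of the five values reaches an action. With ng/mL, each reaches exactly one, and the two lines together fill the header's range. That is the main internal evidence that ng/mL was meant.

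**How the error carries into the hypocalcemia branches.** Take an asymptomatic subject with corrected calcium in the grade 1 range (8.0-8.4 mg/dL) and 25OHD of 25 ng/mL.

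1. The first branch asks whether the 25OHD level calls for more vitamin D. Under the printed lines it does not, because 2500 ng/dL is above both cut-offs.
2. The second branch needs symptoms or 25OHD at the goal of 30 ng/mL. The subject has neither.
3. With the cut-offs in ng/mL, 25 falls in the 20-30 line, vitamin D is to be increased, and the first branch applies.

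The asymptomatic grade 2 branch behaves the same way for a subject not yet at maximum calcium intake.

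**Other explanations.** No text elsewhere corrects or explains the ng/dL unit. A PDF conversion artefact is unlikely, since the unit is right in the header and wrong in both lines below it.

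**The case against.** The strongest reply is that this is a typing slip nobody would act on. The header directly above is in ng/mL, the same 20 and 30 appear elsewhere in ng/mL, calcium and 25OHD are followed in real time, and the team meets weekly on safety data. That stands, and it is why the point is minor. It does not make the printed thresholds right.

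It can also be said that section V promises a strict protocol only for hypocalcemia, whereas the misprinted lines sit under a normal-calcium header. That is fair: they reach hypocalcemia management only through the back-reference.

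Three stronger readings are tempting, and the documents do not support them.

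- A reader might infer a second gap: because the header requires normal calcium, the vitamin D step cannot be used in hypocalcemia, leaving some asymptomatic subjects with no branch. But the grade 1 and grade 2 branches point back to the 25OHD level, not to the header's calcium condition. Importing that condition would make those branches unusable. With the units corrected, no gap remains.
- A reader might therefore want a sentence extending the vitamin D increases to all grade 1 and grade 2 hypocalcemia. That would change treatment: for symptomatic grade 1, section IX orders only more calcium, whatever the 25OHD level.
- A reader might size the problem from the hypocalcemia rate quoted in section VII. That rate describes a different event. The misprinted lines directly govern subjects with low 25OHD and normal calcium, and the documents give no expected number of these.

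**Conclusion.** The point holds and is minor. Both action thresholds are wrong as written by a factor of 100, and as printed no normocalcemic subject with 25OHD above 0.3 and below 30 ng/mL is assigned an action.

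This rests on two assumptions. One is that ng/mL was intended, which the header, the goal and the exclusion limit all support. The other is that the worked values of 15 and 25 ng/mL come with normal corrected calcium, as the header requires.

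A reader might infer that participants would go untreated. The documents do not support that, because the intended unit is plain and a physician sees the results as they come in. The effect is confined to the written safety rules. The CTX and P1NP models, the bone density comparisons and the enrolment of 10 participants do not depend on it.

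**What to change.** In section IX, change ng/dL to ng/mL in both vitamin D action lines, so that they read 20-30 ng/mL and below 20 ng/mL. Leave the header, the doses and the hypocalcemia branches as they are. The back-references then work without further wording.

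The cost is two unit corrections, with no added visits, tests or procedures and no change to the analysis. If staff work from a separate copy of the algorithm, check it for the same slip.
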